To further implicate the role of dysregulated angiogenesis in GI bleeding in CF-LVAD patients, Houston et al. evaluated the use of angiotensin-converting enzyme inhibitor (ACEI) and angiotensin receptor blocker (ARB) therapy in reducing the risk of GI bleeding. Ang-2 expression has previously been shown to be induced through angiotensin II signaling⁹. Houston et al showed that of the patients who did not receive angiotensin II antagonism, 48% experienced GI bleeding. In contrast, only 24% of the patients who received ACEI or ARB experienced GI bleeding¹⁰.

In the most recent J-MACS (Japanese registry for Mechanically Assisted Circulatory Support registry) report, GI bleeding occurred in 4 of 259 patients followed during a 5-year period¹¹. This is in stark contrast to the latest INTERMACS update that reports a rate of 16.24 events of GI bleeding per 100 patient months in the first 3 months after implantation, and 4.08 events per 100 patient months in the 3-12 months after implantation¹². What accounts for this difference? One possibility may lie in the Japanese diet, which is rich in omega 3 fatty acids (O3FA) compared to the diet of patients in the United States. We performed a retrospective study in a cohort of 166 patients with CF-LVAD to assess this theory. Patients who received high-dose O3FA as part of a recovery protocol were compared to those who did not. The frequency of GI bleeding was significantly lower in the O3FA group compared with the control group (0.077 ± 0.419 events/year vs. 0.305 ± 0.847 events/year, $p = 0.033$), leading to a higher 1-year event-free rate in the O3FA group compared to the control group (97% vs. 79%, $p = 0.046$).

In the past decade, there has been an emergence of interest in the human gut microbiota. Using next-generation sequencing (NSG), studies have been able to characterize with great detail the gut microbiome in humans. Further studies have shown that the microbiota is affected by patient characteristics (age, sex, body mass index, lifestyle), diet, and pathologic diseases¹³. In particular, O3FA and its effect on the gut microbiota has been studied, showing that an increase in dietary or supplemental O3FA changes the fingerprint of the microbiome¹⁴⁻¹⁶. O3FA and the microbiome also have a presence in the cancer literature. It is postulated that O3FA play a role in the prevention and treatment of cancer by reduction in cell proliferation, cell survival, angiogenesis, and inflammation¹⁷.

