The data presented thus far shows a possible link between O3FA, GI bleeding, and abnormal angiogenesis, and may be related to the microbiome in CF-LVAD patients. This prospective randomized study aims to evaluate the effect of supplemental O3FA on the frequency of GI bleeding in patients implanted with CF-LVAD both as primary and secondary prevention.

Additionally, we will investigate the effect of O3FA on angiogenesis parameters (Ang-1, Ang-2, VEGF, TNF- α) and the microbiome.

STUDY ENDPOINTS

The primary endpoint will be a change in angiogenesis markers resulting in dysregulated angiogenesis, as described above. Secondary endpoints include rate of GIB and improvement in inflammatory markers.

STUDY INTERVENTION

The study intervention being evaluated is high-dose O3FA (4,000 mg), which is an over-the-counter supplement. Heart failure patients are routinely instructed to take an O3FA supplement for heart health. The research team will fund the supplement, which will be stored in the heart failure office. Once a patient is enrolled, a total of 1 year of supplement will be given to the patient for consumption at home.

PROCEDURES INVOLVED

We will perform an open-label, prospective, randomized control study in which 120 CF-LVAD patients are enrolled. We plan to have 2 separate arms: primary prevention and secondary prevention (60 in each arm). In the primary prevention arm, 60 patients who have received CF-LVAD implantation and have not experienced any episodes of GI bleeding will be assigned to an O3FA group or a control group, with 30 patients in each group. In the secondary prevention arm, 60 LVAD patients who have experienced at least 1 episode of GI bleeding after CF-LVAD implantation will be assigned to an O3FA group or a control group, with 30 patients in each group. Randomization will be performed using computer software, and initiation of therapy will start within 24 hours of randomization. O3FA will be given at a dose of 4,000 mg orally per day, and all patients will receive guideline-directed medical therapy during the study period.

The following study procedures will be performed:

Baseline

Subject to sign consent
Verify inclusion/exclusion criteria
Record medical history and medications
Collect stool sample
Collect blood sample
Randomization
For O3FA subjects:
-Provide O3FA supplement
-Subjects will be instructed to take 4 pills a day

1.5 months post-randomization

Record medical history and medications
Record adverse events

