Statistical analysis will be performed using SPSS Statistics 22 (SPSS Inc, Chicago, IL, USA). Variables with 2-tailed p value <0.05 will be considered significant. Clinical parameters and outcomes including rates of GI bleeding, angiogenesis-related biomarkers, inflammatory markers, and microbiome data will be compared between the O3FA and control groups, both among the primary and secondary prevention arms using unpaired t-test or Mann-Whitney U test as appropriate. A necessary patient number for each group is calculated as 26 (total 104) by power analysis with 0.05 of α , 0.8 of effect size, 0.8 of $1-\beta$.

A master list maintaining patient names and code numbers will be stored in locked files. A password-protected computer located in the heart failure main office will contain a database for data collected in this study. Case report forms (CRF's) will be generated and filled out for each subject enrolled in this study.

There is a risk of loss of confidentiality. If a patient agrees to participate, and signs an informed consent, a signed copy of the consent will be given to them, a copy placed in their record and then the data will be abstracted into an electronic database. The database will be within the Department of Medicine, Section of Cardiology. The data will be password protected and covered by all of the firewalls and security features of the Department of Medicine.

The investigators seek to minimize these risks by labeling the study related data and specimens with a study code. This study code will be linked with the patient's data. Only the investigators

and their designated staff will have access to the databases and the link between study code numbers and patient identifying information.

Data and samples may be utilized by faculties who have the proper IRB approval to do so, and whose study objective meets with the overall objective of this research.

We may share coded data and/or samples outside of the institution in collaboration efforts. An IRB amendment will be submitted to the IRB for review if this happens. Additionally, if NIH funding is obtained for any proposed study, it is possible that the PI will be required to provide a copy of coded data to the NIH for public use. In either case, direct patient identifiers will never be shared.

ECONOMIC BURDEN TO PARTICIPANTS

There will be no economic burden to the participants.

CONSENT PROCESS

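### The GI bleeding rate is compared only by t-test or Mann-Whitney, which weight every patient equally however long each was observed, so the estimated rate can be distorted when follow-up is cut short

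*Combined protocol and SAP*

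**What the plan says.** Study Endpoints lists bleeding as secondary: "Secondary endpoints include rate of GIB and improvement in inflammatory markers". Aim 3 in Objectives asks about bleeding events in both populations.

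The only analysis is one sentence in Statistical Analysis, Data Management, and Confidentiality. It opens with the items to be tested: "Clinical parameters and outcomes including rates of GI bleeding, angiogenesis-related biomarkers, inflammatory markers, and microbiome data will be compared". The contrast is O3FA against control inside each prevention arm, and the method is a choice of two: "using unpaired t-test or Mann-Whitney U test as appropriate". Bleeding is therefore handled exactly like a laboratory measurement.

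The protocol does not say whether the rate is a count or events per year. It does not fix the window: active participation is 1 year, but records are followed for up to 2 years. It gives no person-time denominator, offset or time-to-event method, and no rule for time at risk after death or transplant. The Background reports the team's retrospective cohort as mean and SD of events per year (0.077 ± 0.419 v 0.305 ± 0.847), with the statement that "The frequency of GI bleeding was significantly lower in the O3FA group compared with the control group". Withdrawal of Participants says that the data of withdrawn patients are erased.

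**The concern.** A t-test or Mann-Whitney test needs one number per patient and gives each number the same weight. That suits a biomarker. A bleeding rate carries information in proportion to the time observed, and in this population that time can be cut short: the Background describes bridge-to-transplant use, and patients can die.

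The result depends on which number is used.

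- **Events per year for each patient.** Time enters the denominator but not the weight, so one early bleed in a briefly observed patient can move the group mean a long way.
- **Raw count.** Time is left out altogether, and months after death or transplant are scored as bleed-free.

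At stake is whether the bleeding rates printed for Aim 3 estimate events per patient-year, the kind of unit in which the Background itself quotes the registry. A Mann-Whitney test gives no rate ratio at all.

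**Working it through.** **1. The plan's own figure.** Inputs: effect size 0.8, two-sided α 0.05, power 0.8. The two-sample t-test calculation gives 25.52 per group, rounded up to 26, and 4 × 26 = 104. This agrees with "A necessary patient number for each group is calculated as 26 (total 104) by power analysis". It is a generic two-means calculation with no bleeding rate in it, and nothing below changes it.

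**2. Weight of one patient.** For y bleeds in t years, the mean of per-patient rates is (1/n) Σ(y/t); the person-time rate is Σy / Σt. With n = 30 ("will be assigned to an O3FA group or a control group, with 30 patients in each group"), a patient with one bleed adds (1/t)/30 to the mean:

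- 1 month: 12/30 = 0.40 events/year, more than the whole cohort control rate of 0.305
- 3 months: 4/30 = 0.13
- 12 months: 1/30 = 0.033

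Example: 29 patients, each followed for 1 year, have 9 bleeds in total, and one more patient has 1 bleed in 1 month. Mean of rates: (9 + 12)/30 = 0.70. Person-time rate: 10/29.083 = 0.34.

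**3. Raw counts.** The cohort difference is 0.077 − 0.305 = −0.228. If about 39% of patients end follow-up before 1 year (assumption), the simulated mean difference in counts shrinks to about −0.18.

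**4. Bias of the mean of rates.** Two true rates are used: 0.305 (cohort control) and 0.85, from the registry figures in the Background: (16.24 × 3 + 4.08 × 9)/100 = 0.854 per patient in the first post-implant year. Assumptions not in the documents: 20% leave at a random time in the year, 10% of bleeds end follow-up, gamma overdispersion, and a minimum follow-up (floor). The floor matters because 1/t grows without limit as t approaches 0.

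| True rate | Floor 1 day | Floor 7 days | Floor 30 days | Events / patient-time |
|---|---|---|---|---|
| 0.305 | 0.48 | 0.42 | 0.38 | about 0.30 |
| 0.85 | 1.34 | 1.17 | 1.03 | about 0.82 |

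With 5% of bleeds ending follow-up and a 1-day floor, the means of rates are 0.39 and 1.08. With none, there is no bias.

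**5. Type I error of the planned tests (simulated).** With similar follow-up in both groups it is 3.5–5.4%. With different follow-up (exit hazards 0.1 v 0.7 per year, an assumption) and equal true rates, it is 5.9–7.9% for counts at 0.305/year and 6.2–11.7% at 1.0/year. On per-patient rates it is 6.3–8.1% for Mann-Whitney and 3.8–5.3% for the t-test.

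**6. Power.** 30 v 30, overdispersion 1 to 2, O3FA at about one quarter of control (0.077/0.305 = 0.25). The person-time test takes its p-value from re-randomising group labels.

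| Control v O3FA | Follow-up | t-test on rates | Mann-Whitney | Person-time |
|---|---|---|---|---|
| 0.85 v 0.21 | 20% leave, 10% of bleeds end it | 41–51% | 55–66% | 63–73% |
| 0.85 v 0.21 | 20% leave, no bleed ends it | 57–69% | 53–69% | 61–75% |
| 0.305 v 0.077 | 20% leave, 10% of bleeds end it | 25–29% | 35–40% | 35–39% |
| 0.305 v 0.077 | 20% leave, no bleed ends it | 30–37% | 34–41% | 34–42% |
| 0.305 v 0.077 | complete | 34–44% | 36–46% | 26–33% |

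At 0.85 with complete follow-up, the t-test has 61–78% and the person-time test 57–73%.

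**The case against.** The strongest reply is that the planned tests are serviceable. With similar follow-up in both groups they hold their error rate. Mann-Whitney, which the plan allows, uses ranks, so a briefly observed bleeder takes a top rank but cannot dominate by size. At the sponsor's own cohort rates, a person-time test only matches Mann-Whitney and is clearly weaker when follow-up is complete. All of this stands.

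Four stronger readings are tempting, and the documents do not support them.

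- **Aim 3 loses power, or the tests are invalid.** The power gain appears at 0.85 v 0.21 with early leaving. That 0.85 is a first-post-implant-year figure, whereas the primary prevention arm may enrol up to 3 months after implant, past some or all of the high-rate months. Error inflation needs follow-up to differ between groups.
- **A patient who withdraws at month 2 is scored bleed-free for the rest of the year.** Withdrawn patients' data are erased, so these patients are absent. Short follow-up comes mainly from death, transplant or loss, and record review can continue after visits stop.
- **The INTERMACS definition shows that bleeds end follow-up.** It lists death as one qualifying outcome. That makes it possible but gives no frequency; the 10% is an assumption.
- **The per-patient events-per-year form is fixed.** It is how the retrospective cohort was reported. The trial's own rate is undefined, and on that form time observed is not ignored: it is in the denominator but not in the weight.

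The reply does not answer the point about the estimate. Neither planned test yields events per patient-year or a rate ratio, and erasure does not cover death or transplant.

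**Conclusion.** The point holds as a weakness in how the bleeding rate is estimated. Followed as written, the plan gives a badly weighted rate whenever follow-up varies. One bleed in a patient seen for 1 month counts 12 times as much as one in a patient seen for a year (0.40 v 0.033 in a group of 30), or, with raw counts, unobserved time counts as bleed-free.

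Under the stated assumptions the mean of per-patient rates overstates a true 0.305 by about 25–57% (0.38/0.305 to 0.48/0.305) and a true 0.85 by about 21–58% (1.03/0.85 to 1.34/0.85). The upper ends rest on a 1-day floor. The bias vanishes if no bleed ends follow-up, and the documents give no frequency of early exit.

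A general gain in power is not shown. This is a cheap improvement to a secondary endpoint; it leaves the primary endpoint and the sample size untouched.

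**What to change.** For GI bleeding only, replace the t-test and Mann-Whitney comparison. Suggested content for the analysis section:

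- Within each prevention arm, report for each group the number of bleeding events, the patient-years and the events per patient-year.
- Give the rate ratio, O3FA to control, with 95% CI from a negative binomial model with log(days observed) as offset.
- Time at risk runs from randomisation to the earliest of death, transplant, last contact or the end of the stated window.
- The p-value may come from re-randomising group labels within the arm. This is safer than a model-based p-value with so few events: a robust Poisson model with offset reached 8.7% type I error in one simulated high-overdispersion setting.
- State what is reported if a group has no events. At 0.077/year, 30 patients followed for 1 year expect 30 × 0.077 = 2.31 events, and the Poisson chance of none is exp(−2.31), about 10%; the rate ratio then has no usable model estimate.
- Keep the t-test and Mann-Whitney for biomarkers, inflammatory markers and microbiome measurements.

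**Cost.** Wording in the plan, plus dates. The documents say that events are recorded but do not explicitly say that event dates and end-of-follow-up dates are captured, so the case report form must collect both. Visits, treatment and sample size do not change.

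**Downside.** At 0.85 v 0.21 with early leaving, the re-randomisation test is about 5–20 points more powerful than the planned tests. At 0.305 v 0.077 with early leaving it only matches Mann-Whitney, and with complete follow-up at that rate it gives up about 8–12 points. The sponsor should adopt the change for the estimate and state that trade-off.

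### The Ang-2 comparison leaves out baseline ACEI/ARB use, a recorded and plausible predictor, and so gives up some precision and protection against chance imbalance

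*Combined protocol and SAP*

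**What the plan says.** Under Study Endpoints, "The primary endpoint will be a change in angiogenesis markers". That section does not single out one marker. Ang-2 and VEGF appear both among the angiogenesis parameters at the end of the Background and on the assay list under Blood Collection.

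The Background states that "Ang-2 expression has previously been shown to be induced through angiotensin II signaling". It then reports a cited cohort in which GI bleeding was 48% without and 24% with ACEI/ARB, as support for a role of disordered angiogenesis.

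Procedures Involved adds that "all patients will receive guideline-directed medical therapy during the study period", without naming ACEI/ARB or fixing its use. The baseline list and every later visit list include "Record medical history and medications". Neither the eligibility criteria nor the description of randomisation refers to ACEI/ARB.

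The Statistical Analysis section says that "angiogenesis-related biomarkers, inflammatory markers, and microbiome data will be compared between the O3FA and control groups", separately in the primary and secondary prevention arms, by a two-sample t-test or a Mann-Whitney test. It names no covariate and does not say whether change from baseline or the follow-up level is compared.

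**The concern.** On the protocol's own reasoning, ACEI/ARB use bears on a pathway that feeds one of the primary markers, and the planned test makes no use of it.

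Baseline use can predict the outcome in two ways. If follow-up levels are compared, users and non-users may simply differ. If change is compared, a stable drug effect largely cancels, but a patient who is off the drug at baseline may start it during the year and one already on it cannot. This second route is plausible here because primary-prevention patients enrol up to 3 months after implant and all receive guideline-directed therapy (assumed to include ACEI/ARB). Adjusting for baseline Ang-2 alone need not capture it.

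At stake are some power on a primary-endpoint component and, in a single comparison of 30 v 30, some protection against an uneven split of users. The bleeding comparison is a separate matter and is not covered here.

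**Working it through.** **Inputs from the protocol.** Significance criterion: "Variables with 2-tailed p value <0.05 will be considered significant". Effect size 0.8 SD and power 0.8. Sample size: "A necessary patient number for each group is calculated as 26 (total 104) by power analysis". Planned enrolment is 30 v 30 in each prevention arm.

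**Assumed inputs.** The documents do not give the share p of patients on ACEI/ARB at baseline, nor the shift g (in SD of the analysed Ang-2 outcome) between users and non-users. Ranges are used: p from 0.5 to 0.9, g from 0.3 to 1.0.

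**1. The plan's own figure.** For a two-sided, two-sample t-test at d = 0.8 (noncentral t), power is 79.2% with 25 per group and 80.7% with 26. So 26 is exact for the unadjusted test. At 30 per group, power is 86.1%.

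**2. Chance imbalance at 30 v 30.** The SD of the difference in use is sqrt(2p(1-p)/30), which is 0.129 at p = 0.5. The exact binomial probability of a difference of 20 points or more, in each prevention arm, is:

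| Baseline use | Probability |
|---|---|
| 50% | 15.5% |
| 70% | 12.0% |
| 85% | 4.6% |

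**3. Precision.** The variance explained is R² = p(1-p)g². Adjustment raises the standardised effect to 0.8/sqrt(1-R²), with one degree of freedom lost (49 instead of 50 at 26 per group). For example, p = 0.5 and g = 0.8 give R² = 0.25 × 0.64 = 0.16 and an effect of 0.8/sqrt(0.84) = 0.873.

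| g (SD) | R² at 50% use | Power, n = 26, 50% use | R² at 90% use | Power, n = 26, 90% use |
|---|---|---|---|---|
| 0.3 | 0.0225 | 82% | 0.0081 | 81% |
| 0.5 | 0.0625 | 83% | 0.0225 | 82% |
| 0.8 | 0.16 | 87% | 0.0576 | 83% |
| 1.0 | 0.25 | 90% | 0.09 | 84% |

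The comparator is 80.7% in every row. At 50% use the gain equals 1/(1-R²) - 1 more patients: about 2%, 7%, 19% and 33%. These figures are for the ACEI/ARB term alone. Where baseline Ang-2 already carries part of the same information, the extra gain from this term is smaller.

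**4. False positives with no O3FA effect, 30 v 30, unadjusted t-test (simulated).** Averaged over all randomisations, the rate stays at 5% (simulated 4.8-5.0% at 70% use). Two further cases must be kept apart:

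| g (SD) | Realised chance split, 60% v 40% (18 v 12 users) | Systematic difference, 60% v 40% |
|---|---|---|
| 0.3 | about 5.5% | about 5.5% |
| 0.5 | about 6.0% | about 6.8% |
| 0.8 | about 7.3% | about 9.6% |
| 1.0 | about 8.6% | about 12.0% |

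Repeat runs agree to within about 0.2 points. Both cases shift the contrast by 0.2g. The first is lower because, once the split is fixed, the variation between users and non-users no longer adds to sampling error but still inflates the t-test's denominator. The second describes use that drifts apart by group after randomisation, which adjustment for baseline use does not remove.

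**The case against.** The case for leaving the plan alone is substantial, and most of it stands.

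- **The test is valid.** Randomisation protects the 5% level of the unadjusted comparison, and the sample size was set for that comparison. A reader might infer that the type I error is inflated or that 26 per group is wrong; neither follows.
- **The link is indirect.** A reader might infer that the protocol shows ACEI/ARB lowers Ang-2. It says only that angiotensin II induces Ang-2. The supporting reference is, by its title, work in bovine retinal endothelial cells. The ACEI/ARB outcome data concern bleeding, and no effect on circulating Ang-2 is given.
- **The larger shifts are generous.** For a change score, a 1.0 SD shift by baseline status needs nearly all baseline non-users to start the drug, or a drug effect above 1 SD. The 50% use figure is also the most favourable to adjustment.
- **Ang-2 is not the whole endpoint.** VEGF is on both marker lists too, and the documents link ACEI/ARB to no marker other than Ang-2.
- **The open-label route is not cured.** A reader might infer that, without adjustment, an Ang-2 difference cannot be attributed to O3FA. The documents do not support that: nothing in them suggests ACEI/ARB prescribing would differ by group, and the same background-therapy rule applies to both. Open-label conduct leaves the possibility open, but baseline adjustment would not close it.

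What survives is narrower: a plausible predictor of one primary marker is already recorded at baseline, and using it costs almost nothing.

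**Conclusion.** The point holds as a minor one about efficiency, not as a flaw in validity. The planned Ang-2 comparison ignores baseline ACEI/ARB use although the Background gives a reason to expect it to matter.

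The power gain at 26 per group is at most about 2.5 points for shifts up to 0.5 SD. It reaches about 6 to 10 points only at 0.8 to 1.0 SD with half the patients on the drug, and about 2 to 3.5 points for the same shifts at 90% use. In a trial that happens to split 60% v 40%, the unadjusted false-positive rate is about 5.5% to 8.6% across the assumed range.

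All of this rests on assumed values of p and g, on guideline-directed therapy including ACEI/ARB, and on the t-test rather than the Mann-Whitney option. Confidence in the size is low because the documents give neither value.

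**What to change.** In the Statistical Analysis section, state that Ang-2 will be compared between O3FA and control within each prevention arm by ANCOVA, or by a repeated-measures model over the follow-up samples. Prespecify baseline Ang-2 and baseline ACEI/ARB use (yes/no) as covariates. Including baseline Ang-2 also largely settles whether change or level is analysed, since with that covariate a single-time-point ANCOVA gives the same treatment contrast either way.

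As a descriptive aid only, tabulate ACEI/ARB use by randomised group at the 3-, 6- and 12-month samples. Do not adjust the main analysis for use after randomisation, because open-label assignment may affect it.

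The cost is SAP wording, one table and one degree of freedom per model for the ACEI/ARB term. The medication data are already scheduled for collection, so no extra patients, visits or assays are needed.

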PROTOCOL TITLE

Open-Label Prospective Randomized Control Trial to Investigate the Efficacy of Omega-3 Fatty Acid Therapy in Preventing Gastrointestinal Bleeding in Patients with Continuous-Flow Left Ventricular Assist Device

Version: 05Jun2019

NCT03784963

PROTOCOL TITLE

Open-Label Prospective Randomized Control Trial to Investigate the Efficacy of Omega-3 Fatty Acid Therapy in Preventing Gastrointestinal Bleeding in Patients with Continuous-Flow Left Ventricular Assist Device

PRINCIPAL INVESTIGATOR

[name]
Department of Medicine, Section of Cardiology
[contact]

OBJECTIVES

Aim 1: We will evaluate whether high-dose omega-3 fatty acid (O3FA) supplementation alters markers of angiogenesis and inflammation in patients with continuous-flow left ventricular assist devices (CF-LVAD).

- **Aim 1a** will assess the effect of high-dose O3FA in patients who have not experienced an episode of gastrointestinal (GI) bleeding. Patients will be enrolled up to 3 months following CF-LVAD implantation and randomized to high-dose O3FA or none. Markers of angiogenesis and inflammation will be assessed prior to and following initiation of high-dose O3FA therapy.
- **Aim 1b** will assess the effect of high-dose O3FA in CF-LVAD patients who have already experienced a GI bleeding event. Patients who have experienced a prior bleeding event will be enrolled and randomized to high-dose O3FA or none. Markers of angiogenesis and inflammation will be assessed prior to and following initiation of high-dose O3FA therapy.

Aim 2: We will assess the changes that occur to the microbiome of CF-LVAD patients following O3FA supplementation.

Aim 3: We will assess the effect of high-dose O3FA supplementation on GI bleeding events in both the population without prior GI bleeding events, and the population with prior GI bleeding events.

BACKGROUND

Continuous-flow left ventricular assist devices (CF-LVAD) have become the mainstay of therapy for advanced heart failure, both as bridge to transplantation and as destination therapy, allowing significant improvement in survival. However, this therapy is limited by a high adverse event profile, specifically those related to hemocompatibility.

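### GI bleeding is compared only within each 30 vs 30 prevention arm; add one arm-stratified analysis over both arms, and state that bleeding is not powered at 80% within arms

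*Combined protocol and SAP*

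**What the plan says.** All references are to the combined protocol and SAP.

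- **Analysis.** Under Statistical Analysis, Data Management, and Confidentiality, GIB rates, biomarkers and microbiome data are compared between O3FA and control "both among the primary and secondary prevention arms using unpaired t-test or Mann-Whitney U test as appropriate", at two-sided 0.05. No combined, stratified or time-to-event analysis appears anywhere.
- **Sample size.** The same section states: "A necessary patient number for each group is calculated as 26 (total 104) by power analysis", with effect size 0.8 and power 0.8. It names no endpoint. The total of 104 is 4 x 26, so the planned unit is the comparison within one arm. Procedures Involved plans 30 vs 30 in each arm, 120 in all.
- **Role of GIB.** The title concerns preventing GIB. Aim 3 asks for the effect in "both the population without prior GI bleeding events, and the population with prior GI bleeding events". Study Endpoints makes angiogenesis markers primary and the GIB rate secondary.
- **Prior data.** Background reports a "retrospective study in a cohort of 166 patients with CF-LVAD" with "0.077 ± 0.419 events/year vs. 0.305 ± 0.847 events/year" (O3FA vs control), and 97% vs 79% free of GIB at one year.
- **Follow-up.** The text after Blood Collection records GIB during the one-year study period and also collects outcomes from records for up to two years. It does not say which period the GIB comparison uses, or how a patient's rate is formed when follow-up is short. Study supply of O3FA ends at one year.
- **Withdrawal.** Data of withdrawn participants are erased, including O3FA patients withdrawn for non-compliance.

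**The concern.** GIB is the clinical question, yet the plan splits it into two small comparisons and never brings them together. Each arm will hold few patients who bleed, so even a large true benefit could leave two non-significant results, which are easily misread as no effect. A combined analysis chosen after the data are seen would carry little weight, so it has to be named in advance. The one power statement gives the reader no way to see that it does not speak to GIB.

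**Working it through.** **1. The plan's own figure.** Two-sided t-test, d = 0.8, alpha 0.05 (noncentral t): power 0.791 at n = 25, 0.807 at n = 26, 0.861 at n = 30. So 26 per group reproduces. It fits one continuous variable compared within one arm.

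**2. The same test on the Background GIB rates.** Pooled SD = sqrt((0.419² + 0.847²)/2) = 0.668. d = (0.305 − 0.077)/0.668 = 0.341. Power is 0.255 at 30 vs 30 and 0.458 at 60 vs 60.

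**3. Simulation on counts.** The counts are skewed, so d alone does not fix power. Each patient's rate was drawn from a gamma distribution with shape k and the bleeds from a Poisson distribution (6,000 trials per setting, one year of follow-up, equal rates and effect in both arms). The Background SDs are treated as those of one-year counts, so k = mean²/(SD² − mean):
- control: 0.305²/(0.847² − 0.305) = 0.226
- O3FA: 0.077²/(0.419² − 0.077) = 0.060

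The event-free proportion is (1 + mean/k)^(−k). With these k it is 82% and 95%, not the reported 79% and 97%. Matching those needs k = 0.476 and 0.019. Three settings are therefore shown for the Background cohort: k = 0.226 in both groups, SD-matched, and event-free-matched.

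The registry rates in Background give two higher control rates. The rate after month 3 is 12 x 4.08/100 = 0.49 per year. With the early rate ("16.24 events of GI bleeding per 100 patient months in the first 3 months after implantation") the first year gives (3 x 16.24 + 9 x 4.08)/100 = 0.85. The early period is relevant because Aim 1a says "Patients will be enrolled up to 3 months following CF-LVAD implantation". For these, k is 0.226 or an assumed 0.5.

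Power at rate ratio 0.25, in %:

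| Control rate per year | One arm: t / Mann-Whitney / log-rank | Both arms: t / Mann-Whitney / stratified log-rank |
|---|---|---|
| 0.305, common k | 23 / 28 / 27 | 53 / 49 / 48 |
| 0.305, SD-matched | 26 / 36 / 37 | 53 / 63 / 63 |
| 0.305, event-free-matched | 47 / 61 / 63 | 64 / 90 / 90 |
| 0.49, k = 0.226 | 29 / 31 / 31 | 64 / 56 / 54 |
| 0.49, k = 0.5 | 48 / 47 / 45 | 83 / 77 / 75 |
| 0.85, k = 0.226 | 37 / 35 / 33 | 75 / 63 / 58 |
| 0.85, k = 0.5 | 63 / 58 / 54 | 94 / 88 / 83 |

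Type I error was 0.04-0.055 for every test. Over both arms the log-rank test never exceeds Mann-Whitney and is below the t-test in five of seven rows. Combining the arms produces the gain.

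**4. A smaller effect (assumed rate ratio 0.5).** With the control rates above: 9-24% in one arm, 18-34% over both. If the Background risks of 35.1% and 40% are taken as one-year control risks without overdispersion, both arms give about 48% and 54%. With assumed control risks of 25% and 40% and hazard ratio 0.5, the arms give 22% and 31%, and both together 46%. Rounded outward: about 10-35% in one arm and 15-55% over both.

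**5. Sensitivity of the stratified log-rank test, three 0.305 settings in order.**
- Assumed 25% early loss: 44%, 57%, 86%.
- Assumed 20% of O3FA patients erased at random: 39%, 55%, 85%.
- Effect in one arm only: 13%, 16%, 24% over both arms, against 28%, 36%, 62% within that arm.

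**6. No bleeder in the O3FA group.** At 97% event-free, 0.97^30 = 0.40 in one arm and 0.97^60 = 0.16 over both. An ordinary hazard or rate ratio cannot then be estimated.

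**7. False positives.** Two by-arm tests: 1 − 0.95² = 9.8%. Adding the combined test, which is correlated with both, gives about 11.5%.

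**The case against.** The design calls the arms separate, Aim 3 names two populations, GIB is secondary, and no GIB power is promised. On that view a combined test is a preference, and it dilutes the effect if only one population benefits. This stands as a limit on the claim: the by-arm results must stay, and the combined result must not be called confirmatory.

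It also stands that time to first bleed is not the more powerful choice. It ignores repeat bleeds and usually trails pooled counts, not only when bleeding is frequent. Its justification is that censoring deals with unequal follow-up; the tests were not compared under loss. Since the stated endpoint is a rate, the rate ratio belongs beside it.

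Three stronger readings are tempting and are not supported:
- *The sample size is wrong, or GIB is claimed to have 80% power.* The arithmetic reproduces, and no such claim is made.
- *The 26 per group is for one marker.* That is a reasonable guess, but no document says so.
- *A single arm could not detect the retrospective effect.* In the event-free-matched setting one arm has 61-63% power by Mann-Whitney or log-rank.

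**Conclusion.** The point holds as a cheap improvement. Only within-arm GIB comparisons are planned. At rate ratio 0.25 these have about 20-65% power, against about 50-90% for an arm-stratified analysis of both arms. At an assumed rate ratio of 0.5 the figures are about 10-35% and 15-55%, so combining helps but does not make GIB confirmatory.

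The ranges assume full accrual of 120, an equal effect in both arms, and Background SDs that describe one-year counts (no follow-up time is given). The bleeding rate in the secondary-prevention arm is not given either, and a retrospective effect may be overstated. Erasing the data of non-compliant O3FA patients can bias the GIB comparison. Combining the arms does not remove that bias; it would only estimate a possibly biased contrast more precisely.

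**What to change.** **Analysis text.** Keep the by-arm comparisons. Add one prespecified GIB analysis over all randomised patients whose data are retained, stratified by prevention arm, to 12 months from randomisation, with year 2 reported separately. Specify:
- a stratified log-rank test of time to first bleed;
- the arm-stratified bleed rate ratio per follow-up time, with 95% CI;
- numbers bled and the 12-month bleed-free proportion in each group;
- a penalised or exact method, named in advance, in case an O3FA group has no bleeder;
- how death, transplant and device removal are handled in the analysis (for example as censoring, with a competing-risk sensitivity analysis);
- the number erased per group, with a statement that the erasure can bias the comparison.

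**Sample-size text.** Name the endpoint for the 26 per group, and say that GIB is not powered at 80% within arms. If GIB power is printed, give it as a range with its assumptions.

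**Cost.** Wording and standard methods; no more patients or visits. A penalised or exact method may need software besides SPSS 22. There are three downsides. The combined estimate averages two prevention settings and loses power if only one benefits (13-24% against 28-62%). A third test raises the chance of at least one false positive from 9.8% to about 11.5%, so the p-values should be called nominal. First-bleed analysis discards repeat bleeds, which is why the rate ratio is reported with it.
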